9.4 Methods of Analysis

9.4.1 Analysis of Primary Objective

RNA from a set of 60 samples (30 at baseline and 30 at week 24) will be isolated, amplified, labeled and hybridized on the Sentrix Human-6 Expression BeadChip containing approximately 38,000 probes per chip. The Illumina platform will be used which is a one-color platform using cye 3. Initially, filtering and pre-processing methods will be performed on the 38,000 genes in order to eliminate genes that are poorly measured or that exhibit aberrant values.

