1.0 STUDY OBJECTIVES

1.1 Primary Objectives

1.1.1 To characterize changes in gene expression profiles associated with early (week 4) and late (week 24) MVC therapy intensification.

1.1.2 To evaluate the association of gene expression profiles induced by MVC on the rate of CD4+ T-cell recovery during MVC therapy intensification.

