It is well-recognized that the chemosensitivity and prognosis of some cancers is correlated with specific gene-expression profiles [33, 34], however, our understanding of host gene interactions with HIV during antiretroviral therapy and the impact on CD4⁺ T-cell recovery is at an early stage. Li et al. performed functional genomic analysis to identify treatment-responsive genes in HIV-infected patients initiating ART [35]. Genomic chip arrays were used to screen approximately 12,000 human genes of which ~ 200 genes' expression appeared to be modified in response to HIV therapy. Genes involved in T-cell apoptosis, immune activation and some chemokines and cognate receptors (i.e. CCR5, MIP-1 β , RANTES and others) were down-regulated, while genes involved in tissue repair and remodeling were up-regulated.

Based upon the biology of CCR5 and its role in HIV infection [36] and ART-responsive gene expression profiles observed by Li et al. [35], we have selected candidate genes involved in immune function whose expression may be further altered during CCR5 intensification. We hypothesize that expression will decrease among genes involved in immune activation (NF- κ B, MAPK, nuclear factor of activated T-cells, MYD88 and STAT1), apoptosis (Fas ligand and TRAIL) and trafficking/repopulation of T-cells (CCR5, MIP-1 α , MIP-1 β and RANTES) and increase among genes involved in tissue repair (platelet-derived growth factor,

insulin-like growth proteins and osteoblast-specific transcription factor) (**Figure 1**).

Figure 1. Model of gene expression due to anti-inflammatory affects of Maraviroc in combination with suppressive antiretroviral therapy

Chemokine receptors and their ligands are both redundant and pleiotropic in function and may have a varied spectrum of biologic activities in vivo which may not be represented by a small set of selected gene candidates. Further gene expression profiles of peripheral blood mononuclear cells differ from T-lymphocyte subsets [37]. Therefore, whole genome expression (38,000 genes) will initially be done on purified CD4+/CD8+ T-cells at baseline, week 4 and at week 24 of MVC intensification.

Use of MVC is indicated in combination with other antiretroviral agents for treatment-experienced adult patients infected with detectable CCR5-tropic HIV-1 virus and evidence of multi-drug resistant virus. The manufactures of MVC recommend that the following points should be considered when initiating therapy with MVC:

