3.5 Microarray analysis

Whole genome expression (38,000 genes) will initially be done on purified CD4+/CD8+ T-cells at baseline, week 4 and at week 24 of MVC intensification. However, considering that other immune cells, such as monocytes, also express CCR5 these cells will be stored for future microarray analyses.

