6.1 Schedule of Events – Clinical Evaluations

	Screening	Pre-Entry	Entry	Maraviroc Therapy Intensification (24 weeks)					Post-Maraviroc Intensificatoin	Treatment Failure, Tox or Premature D/C
	Within 30 days of entry	> 48 hrs before entry	Day 0	Week 2	Week 4	Week 8	Week 12	Week 24	Week 36	
Informed Consent	X									
Medical/Medication History	X									
Documentation of HIV	X									
Clinical Assessment / AE			X	X	X	X	X	X	X	X
Documentation of within criteria HIV RNA and CD4 prior to screen labs	X									
Complete Physical Exam			X							X
Targeted Physical Exam							X	X	X	
Start and Dispense Drug			X		X		X			
Stop and Collect Drug								X		X
Concomitant Medications	X		X	X	X	X	X	X	X	X
Adherence Assessment	X		X	X	X	X	X	X	X	X

CCTG 590
Protocol version 1.0
August 13, 2008

Schedule of Events – Laboratory Evaluations

	Screening	Pre-Entry	Entry	Maraviroc Therapy Intensification (24 weeks)					Post-Maraviroc Intensification	Treatment Failure, Tox or Premature D/C
	Within 30 days of entry	> 48 hrs before entry	Day 0	Week 2 (± 1 wk)	Week 4 (± 1 wk)	Week 8 (± 2 wk)	Week 12 (± 2 wk)	Week 24 (± 2 wk)	Week 36 (± 2 wk)	
Hematology (local lab)	X		X	X	X	X	X	X	X	X
Prothrombin time (local lab) †	X									
Chemistry / LFT (local lab)	X				X		X	X	X	X
Pregnancy test (local lab)	X	And anytime when suspected								
CD4+/CD8+ (local lab)	X		X	X	X	X	X	X	X	X
§ CD4 ≤ 350; HIV RNA ≤ 50	X									
Plasma HIV-1 RNA PCR (local lab)	X		X		X			X	X	X
Plasma for MVC levels †			X		X			X		
Extended flow cytometry & PBMC collection (UCSD lab)		X	X		X			X		
Microarray - PBMCs collection (local processing in real-time)			X		X			X		
Lumbar puncture†			X		X			X		
Plasma for storage			X		X			X	X	
Serum for storage			X		X			X	X	
Ship ambient sample for extended flow in real-time		X	X		X			X		
Ship frozen all stored PBMCs, plasma and serum									X	
HIV Resistance & Tropism testing										X

§ If available within 30 days of screen then do not need to repeat laboratory test and can use value obtained within 90 days as screen value

† Only for subjects co-enrolled in the central nervous system sub-study

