6.2.11 Microarray Studies

Blood for PBMCs for microarray studies will be collected at entry and weeks 4 and 24. Specimens will need immediate on-site processing and storage. All

specimens must be **shipped overnight, frozen to the central laboratory (UCSD)** on week 36.

Blood volume: 30 mL

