9.2 Endpoints

9.2.1 Primary

1. Differences in gene expression profiles obtained at baseline and weeks 4 and 24.

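### The primary analysis leaves out the week-4 arrays that the primary objective and endpoint include, and primary objective 1.1.2 has no analysis

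*Combined protocol and SAP*

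**What the plan says.** **Objectives (1.1).** Objective 1.1.1 is "To characterize changes in gene expression profiles associated with early (week 4) and late (week 24) MVC therapy intensification". Objective 1.1.2 is "To evaluate the association of gene expression profiles induced by MVC on the rate of CD4+ T-cell recovery during MVC therapy intensification".

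**Primary endpoint (9.2.1).** There is one: "Differences in gene expression profiles obtained at baseline and weeks 4 and 24".

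**Design and collection.** Section 2.3 says that "whole genome expression (38,000 genes) will initially be done on purified CD4+/CD8+ T-cells at baseline, week 4 and at week 24 of MVC intensification". Section 3.5 repeats the three visits ("at baseline, week 4 and at week 24 of MVC intensification"), and section 3.1 also places arrays at weeks 4 and 24. The laboratory schedule in 6.1 marks the microarray draw at entry, week 4 and week 24. Section 6.2.11 agrees: "Blood for PBMCs for microarray studies will be collected at entry and weeks 4 and 24".

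**Primary analysis (9.4.1).** "RNA from a set of 60 samples (30 at baseline and 30 at week 24) will be isolated, amplified, labeled and hybridized". Section 9.4.1.2 puts 20 baseline and 20 week-24 samples in the training set and the other 10 and 10 in the test set. Significance Analysis of Microarrays (SAM) then ranks genes on the difference between those two visits. The sample size in 9.3 also rests on baseline to week 24 only.

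**Secondary analyses (9.4.3.1).** Item 3 compares PI/r with NNRTI subjects at baseline, week 4 and week 24, using gene lists from the primary analysis. Item 5 correlates early immune-subset change with CD4 recovery.

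**The concern.** There are two separate gaps.

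The first is a contradiction. The objective, endpoint, rationale, design and collection schedule all treat week-4 expression as primary, while the primary analysis neither hybridises nor tests week-4 samples. Any week-4 contrast produced later would be unplanned, although it answers half of objective 1.1.1. Week 4 is also the on-maraviroc array visit that the replacement rule protects: subjects who stop before week 4 are replaced (6.2.3) and those who stop later are not (6.2.4). Item 3 inherits the gap, because it needs week-4 gene lists that the primary analysis does not generate.

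The second is an omission. Objective 1.1.2 links expression to the rate of CD4 recovery, and hypothesis 1a in 2.3.1 restates it. The plan gives no test, does not say which expression change enters, and sets no error rate for a search over about 38,000 probes. A result reported for 1.1.2 could not be called prespecified.

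**Working it through.** **1. Array count.** Inputs: 30 subjects (3.1); two visits in 9.4.1; three visits in 9.2.1.

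- As analysed: 30 × 2 = 60, which reproduces the plan's figure and shows that no week-4 array is counted.
- As the endpoint requires: 30 × 3 = 90.
- Shortfall: 90 − 60 = 30 arrays, or 30/90 = one third.

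**2. Room in the training/test split.** Section 9.4.1.2 allocates 20 + 20 + 10 + 10 = 60, so every hybridised sample is used and none is from week 4. With week 4 included and subjects kept whole, the split is 20 × 3 = 60 training and 10 × 3 = 30 test arrays.

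**3. Is the existing power table sound?** Inputs from 9.3: unpaired Wilcoxon rank sum test, type 1 error 0.01, 2-fold change, biological SD 0.4, technical SD 0.3 or 0.4, signal-to-noise 2 or 3. The table was simulated with 150,000 replicates. Each value was signal × exp(biological + technical error) plus unit-variance noise, with the two group means centred on the stated signal-to-noise ratio and a two-sided test. The noise model, the centring and the two-sidedness are inferred, because 9.3 names only an on-line calculator.

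| N per visit | Technical SD | Signal-to-noise | Stated | Recomputed |
|---|---|---|---|---|
| 20 | 0.3 | 3 | 77% | 76.5% |
| 20 | 0.4 | 3 | 68% | 66.7% |
| 20 | 0.3 | 2 | 61% | 60.0% |
| 25 | 0.3 | 3 | 88% | 87.9% |
| 25 | 0.4 | 3 | 80% | 79.8% |
| 25 | 0.3 | 2 | 75% | 74.0% |

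All six rows agree within 2 points. The table holds for baseline versus week 24. It would carry over to week 4 versus baseline only if the same 2-fold effect and SDs are assumed there.

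**4. Does anything in 9.4 answer 1.1.2?**

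| Analysis | What it relates | Expression against CD4 rate? |
|---|---|---|
| SAM (9.4.1.2) | expression and visit | No |
| Clustering and shrunken centroids (9.4.1.2) | expression and classes found by clustering | No |
| Item 1 mixed model | CD4 count and time, period | No |
| Item 2 mixed model | CD4 count and time, regimen | No |
| Item 3 | gene lists and regimen | No |
| Item 5 | immune subsets and CD4 recovery | No |

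The remaining items cover immune markers, CSF measures, toxicity and virologic failure. Section 9.1 lists expression change and CD4 slope as two separate associations with maraviroc and does not join them. Section 2.3 promises only that a model will be outlined from the literature and the observed immune responses, which is a narrative and not a test. The documents give no effect size or error rate for 1.1.2, so no power figure can be derived for it.

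**The case against.** The strongest reply is that 9.4.1 is incompletely worded and the analysis is not truly missing. The visits, blood draws, pre-processing and SAM procedure all exist, and item 3 presupposes week-4 gene lists, so the authors probably meant the same procedure to run at week 4. That may be so, but the text does not say it. Section 9.4.1 gives an explicit count, the split uses all of it, and 9.3 sizes the same single contrast. Nor is week 4 deferred: what 3.5 stores for future arrays is other immune cells such as monocytes.

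Three parts of the reply do stand:

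- Week-4 arrays have a stated use, the regimen comparison in item 3. That comparison does not set week 4 against baseline.
- The CD4 outcome for 1.1.2 is largely fixed. The objective specifies the rate during intensification, and 9.1 measures recovery by CD4 slope. The linking test and its error rate are what is missing.
- This is a single-arm pilot, so a result for 1.1.2 would be hypothesis-generating in any case. The sponsor nevertheless made it a primary objective.

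A reader might also infer that 1.1.2 would be tested probe by probe with no multiplicity control, and so yield many chance findings. The documents do not support this. The no-adjustment statement in 9.4.3.1 governs secondary analyses, the Pearson correlation in item 5 is for immune subsets, and for expression data 9.3 and 9.4.1.2 point to false discovery rate control.

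**Conclusion.** Both gaps hold and must be fixed before analysis. One of three primary-endpoint time points is absent from the primary analysis, and one of two primary objectives has no analysis. The first is a contradiction between sections that must be reconciled, and it can be closed by wording alone if the sponsor prefers. The second is a missing method.

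A reader might conclude that the primary analysis as a whole is unsound. It is not: the baseline to week-24 comparison is specified and its power table reproduces.

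The count of 60 against 90 assumes one array per subject and visit, as 9.4.1 implies. If CD4+ and CD8+ cells were arrayed separately, which the documents do not settle, it would be 120 against 180, with the same one-third gap.

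**What to change.** **(a) Week 4.** Amend 9.4.1 to 90 arrays, pre-processed together. Keep all of a subject's samples in one set (20 subjects for training, 10 for testing). Run the stated SAM procedure as two paired contrasts, week 4 minus baseline and week 24 minus baseline, with the 2% false discovery rate applied to each, because 1.1.1 asks about early and late change separately. If the week-4 arrays will not be run, remove week 4 from 1.1.1, 9.2.1 and item 3, and align 2.3, 3.1 and 3.5.

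**(b) Objective 1.1.2.** Prespecify one lead analysis: SAM with a quantitative response, relating each subject's log2 expression change from baseline to week 24 to that subject's on-maraviroc CD4 slope, at the 2% rate of 9.4.1.2. Other methods would serve, provided that one is named in advance.

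- *Slope:* define it once. Item 1 uses baseline, week 4 and week 24, whereas 6.1 schedules counts at entry and weeks 2, 4, 8, 12 and 24. Either use item 1's time points or amend item 1 to use all scheduled on-maraviroc counts.
- *Subjects:* include everyone with both arrays. This may be fewer than 30, since subjects who stop after week 4 are not replaced.
- *Supportive analyses:* the week-4 expression change, and the on-maraviroc minus pre-maraviroc slope difference (hypothesis 1a concerns an increase in the rate, and 3.1 already commits to a pre-maraviroc rate per subject).
- *Label:* the whole analysis is hypothesis-generating.

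**Cost.** Up to 30 arrays beyond the 60 in 9.4.1, already committed in 3.1 and 3.5, plus SAP wording and analysis time. No new subjects, visits or CD4 tests are needed. The week-4 fallback costs only wording but gives up the primary result on early change.

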9.4.1.1 Pre-processing

Microarray data will be pre-processed via the Robust Multichip Average (RMA) method [54], as implemented in Bioconductor [55], a suite of programs, for the R statistical programming language [56]. RMA pre-processing consists of three steps: background adjustment, normalization, and summarization [54]. The RMA background noise adjustment corrects for processing effects and cross-hybridization by using a convolution model [54]. The purpose of normalization is to reduce the non-biological variation across the chips in an experiment. Non-biological variation includes technical variability, which is related to the experimental procedure of the assay. RMA uses the quantile normalization technique to adjust the gene expression intensities such that the distributions of the probe intensities are the same across all chips [57]. The last step, summarization, is a method to calculate a single gene expression value by mathematically combining the probe intensities from each probe set. RMA employs the robust multi-chip linear model fitted on a log scale [58].

9.4.1.2 Statistical Analysis

We expect to eliminate approximately 2-3% of genes in through pre-processing and filtering. The data will be randomly divided into a separate training set and a test set. 20 Baseline and 20 Week 24 samples will be used for training. The remaining 10 baseline and 10 week 24 samples will be used for testing. Using criteria such as 2-fold differences in gene expression between the two measured time points within the group of patients and a false discovery rate (the percentage of genes that will be identified by chance) of less than 2%, Significance Analysis of Microarrays (SAM) [59]) will be applied to the training set to rank order genes that best can predict differences in gene expression profiles between the two time points. The SAM method identifies genes with statistically significant changes in expression by computing a score for each gene relative to the gene specific standard deviation. Genes with scores greater than a certain (adjustable) threshold will be declared significant.

The set of highest ranking genes identified with the SAM procedure will then be clustered using unsupervised hierarchical clustering analysis [60]. The purpose of this clustering analysis is to confirm the results from SAM and to further explore the microarray data in order to possibly reveal unknown subclasses. In unsupervised hierarchical clustering, no predefined reference vectors are used and the data is not partitioned into a particular cluster in a single step. Instead, a series of partitions takes place. Next, we will use methods such as prediction analysis of microarrays (PAM) based on nearest shrunken centroids [61] to devise a cross-validated gene expression predictor for these cluster-defined classes. The PAM method is a modification of the more standard nearest-centroid method. Each class centroid is shrunk toward the overall centroids after standardizing by the within-class standard deviation. The test set will then be used for validation of our

predictor. The genes that best predict the classes will be examined for similarities such as possibly participating in common genetic pathways.

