9.3 Sample Size and Accrual

Sample size calculations are based on within-patient comparisons of gene expression profiles from baseline to week 24. The calculations required to make such comparisons will depend on several experimental parameters including biological variability of the samples within each class, the expected fold change to be detected, technical sensitivity of the microarray technology, and acceptable error rates of the results. As researchers in this field have shown [52], one way to ensure acceptable error rates is to control the false discovery rate (FDR), which is

equivalent to setting a minimum specificity. The FDR is the expected fraction of significant genes, which in practice, do not differ in reality. This differs from the false positive rate (FPR), which is the proportion of non-differentially expressed genes that, just by chance, appear to differ.

Determining the biological variability of the system is a difficult task, especially when there is no pre-existing data available. The ranges of conditions that can contribute to biological variability include environmental conditions, cell types, and genotypic variation [53]. Based on an extensive literature review, Zien et al. [53] conclude that a value of 0.4 provides a conservative estimate of the biological standard deviation (variability between and within classes of biological samples). We will consider biological standard deviation values of 0.4 for our power calculations. Further, we will consider a technical variation of 0.3 and 0.4.

As a conservative approach, we base the sample size calculations on the Wilcoxon Rank Sum test. This is a non-parametric procedure, in which no distributional assumptions are placed on the data. Using the on-line power calculator developed by Zien et al. [53] which computes sample sizes for microarray experiments, Table 1 provides the approximate statistical power for various biological variation, technical variations and signal-to-noise ratios. Here, we consider a Type 1 error of 0.01 and a fold change of 2. We assumed 500 hits from the 38,000 genes. Notice that these power calculations are based on the number of samples allocated to the training set (either 20 or 25 per group). The sample size calculations indicate fair power (60-80%) to find a difference in gene expression before and after maraviroc treatment.

Baseline (N)	Week 24 (N)	Biological Variation	Technical Variation	Signal-to-noise	Power
20	20	0.4	0.3	3	77%
20	20	0.4	0.4	3	68%

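### SAM, the only specified test of the primary endpoint, is run on 20 of the 30 samples per time point, although only the later predictor needs a hold-out

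*Combined protocol and SAP*

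**What the plan says.** The primary endpoint in 9.2.1 is "Differences in gene expression profiles obtained at baseline and weeks 4 and 24". Section 9.4.1 plans "RNA from a set of 60 samples (30 at baseline and 30 at week 24", so 30 arrays are available at each of the two time points that it analyses.

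Section 9.4.1.2 then divides these at random. For the larger part, "20 Baseline and 20 Week 24 samples will be used for training"; for the rest, "The remaining 10 baseline and 10 week 24 samples will be used for testing". SAM "will be applied to the training set to rank order genes that best can predict differences in gene expression profiles between the two time points", with selection criteria that include a 2-fold difference and "a false discovery rate (the percentage of genes that will be identified by chance) of less than 2" per cent. The top-ranked genes go into hierarchical clustering, and PAM builds a predictor of the resulting classes. The held-out samples have one stated role: "The test set will then be used for validation of our" predictor. No other test of the primary endpoint is given in 9.4.1.

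Section 9.3 is open about the basis of its table: "Notice that these power calculations are based on the number of samples allocated to the training set (either 20 or 25 per group". The table assumes a Wilcoxon rank-sum test, a type 1 error of 0.01, a fold change of 2 and 500 true hits among 38,000 genes.

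**The concern.** One SAM run serves two purposes. The first is to find genes whose expression changes between baseline and week 24, which is the primary endpoint. The second is to select features for a predictor. Only the second needs untouched samples. For the first, the error rate is controlled through the FDR, and that holds on the full set of arrays as well as on a subset.

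As written, the endpoint for which the study is powered carries the cost of the predictor's hold-out. Genes that respond to maraviroc are more likely to be missed, and each estimated fold change is less precise than the collected arrays allow. The loss carries over to item 3 of the secondary analyses (9.4.3.1), which compares the primary gene lists by regimen type.

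The power table has a related fault. Half of its rows are for 25 per group, but 9.4.1.2 fixes training at 20, so those rows describe no planned analysis.

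**Working it through.** **Inputs.** From 9.3: power at 20 per group of 77%, 68% and 61%; at 25 per group of 88%, 80% and 75%; alpha 0.01; 500 true hits among 38,000, hence 37,500 nulls. From 9.4.1 and 9.4.1.2: 30 samples per time point, 20 of them for training. The sidedness of alpha is not stated; two-sided reproduces the table.

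**Step 1. Reproduce the plan's own figures.** With z = 2.576, back out the non-centrality at 20 per group as nc20 = 2.576 + z(power):

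- 77%: 2.576 + 0.739 = 3.315
- 68%: 2.576 + 0.468 = 3.044
- 61%: 2.576 + 0.279 = 2.855

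Scale to n per group by nc20 × √(n/20); power is Φ(nc − 2.576). At 25 this gives 87%, 80% and 73%, against the table's 88%, 80% and 75%. The scaling therefore follows the plan's calculator to within 2 points.

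A simulation of the rank-sum test (multiplicative log-normal biological and technical error plus additive noise set by the signal-to-noise ratio) also reproduced all six rows to within 2 points. The documents do not give the calculator's error model; that form was found by trying variants.

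**Step 2. Use all pairs on the same basis.**

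| Per time point | Row 1 | Row 2 | Row 3 |
|---|---|---|---|
| 20 (table) | 77% | 68% | 61% |
| 24 (assumed 20% loss) | 85% | 78% | 71% |
| 27 (assumed 10% loss) | 90% | 83% | 77% |
| 30 (no loss) | 93% | 88% | 82% |

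For row 1 at 30: 3.315 × √1.5 = 4.060, and Φ(4.060 − 2.576) = 0.931. The simulation gives 94%, 89% and 83% at 30.

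**Step 3. Precision.** The ratio of standard errors is √(20/30) = 0.816, a cut of 18%. With 27 pairs it is √(20/27) = 0.861 (14%); with 24 it is √(20/24) = 0.913 (9%).

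**Step 4. What these powers are not.** At alpha 0.01 the 37,500 nulls yield 0.01 × 37,500 = 375 expected false positives. The implied FDR at 20 per group is 375/(375 + 500 × 0.77) = 49% for row 1 and 375/(375 + 500 × 0.61) = 55% for row 3. The plan asks for less than 2%. Solving a × 37,500 / (a × 37,500 + 500 × power(a)) = 0.02 with the non-centralities above gives:

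- at 20: a from 2.3e-5 to 6.9e-5, power 8% to 25%
- at 30: a from 9.2e-5 to 1.7e-4, power 34% to 62%

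The simulated model gives about 24% to 55% at 30. All these figures treat the two time points as independent groups. A paired analysis could differ, but the documents give no within-subject correlation. They also precede any filter on the observed fold change: a gene whose true change is exactly 2-fold passes an observed 2-fold cut about half the time at any sample size.

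**The case against.** The strongest reply is that this is a disclosed trade-off in a self-described pilot. Section 9.3 says that power rests on the training set, a gene classifier is a declared goal (2.1, goal 4), and gene selection for that classifier must stay inside the training samples. This stands in part. The held-out arrays are put to legitimate use, and a reader who infers that a third of the data is thrown away goes too far. It does not justify tying the primary gene list to the same run, because a second SAM run on all pairs takes nothing from the predictor.

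A reader might also infer that 82-93% power is available for the primary analysis. The documents do not support that. The figures belong to an unpaired rank-sum test at per-gene alpha 0.01, not to SAM at FDR below 2%. They also need 30 complete pairs, while subjects who stop treatment after week 4 are not replaced (6.2.4) and 9.3 states no allowance for loss.

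Nor can one say that SAM uses exactly 20 of the 30 subjects. Section 9.4.1.2 divides samples and does not say that both samples of a subject stay together.

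Finally, the SAM threshold is described as adjustable. If it were tuned on all pairs and then carried into the predictor, the test subjects would have influenced selection. That is a fair warning about the remedy, and the fix allows for it.

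**Conclusion.** The point holds as one of efficiency. The only specified test of the primary endpoint uses two thirds of the available arrays, and the hold-out does nothing for that test. Using all pairs would cut standard errors by up to about 18%. On the table's own basis, power would rise from 61-77% to about 82-93% with 30 complete pairs, 77-90% with 27 or 71-85% with 24; the two loss rates are assumptions. At the planned 2% FDR the absolute power is much lower, but the relative gain is larger: from roughly 8-25% to 34-62%. That range rests on the unpaired approximation and on the plan's figure of 500 true hits.

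A reader might take this as a flaw in validity. It is not: FDR control is as sound on 20 samples per time point as on 30. The mismatch between the 25-per-group rows in 9.3 and the fixed training size in 9.4.1.2 is a plain inconsistency and should be removed.

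**What to change.** **In 9.4.1.2:**

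- Run SAM on all evaluable baseline/week 24 pairs for the primary gene list, with the FDR and fold-change thresholds fixed in advance.
- For the predictor only, keep a 20/10 split made by subject, so that both samples of a subject fall on the same side. Repeat gene selection inside the 20 training subjects so that the test set stays untouched.

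**In 9.3:**

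- Remove the 25-per-group rows.
- Keep the 20-per-group rows, labelled as the predictor's training set.
- Add an all-pairs row with an attrition case.
- State that the figures are for a rank-sum test at alpha 0.01, or restate them at the planned 2% FDR. The 82-93% range should not appear as power of the primary analysis.

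**Cost:** changes of wording, one more SAM run, and two gene lists to report and keep distinct. No further samples, arrays or visits are needed.

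### The 60-80% power in section 9.3 omits the observed 2-fold cut named in section 9.4.1.2, which caps selection of a truly 2-fold gene at about 50%

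*Combined protocol and SAP*

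**What the plan says.** Section 9.1 says the study is powered on gene expression, and section 9.2.1 makes it the primary endpoint. Section 9.3 holds the only power statement.

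- Test: "we base the sample size calculations on the Wilcoxon Rank Sum test".
- Error rate and effect: "Here, we consider a Type 1 error of 0.01 and a fold change of 2".
- Variability: "We will consider biological standard deviation values of 0.4 for our power calculations". "Further, we will consider a technical variation of 0.3 and 0.4". The table adds signal-to-noise ratios of 3 and 2.
- Prevalence: "We assumed 500 hits from the 38,000 genes".
- Result: "The sample size calculations indicate fair power (60-80%) to find a difference in gene expression before and after maraviroc treatment". The table rows are 77, 68 and 61% with 20 samples per time point, and 88, 80 and 75% with 25.

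Section 9.4.1.2 assigns 20 baseline and 20 week 24 samples to training and applies Significance Analysis of Microarrays (SAM) to them. It describes the selection as "Using criteria such as 2-fold differences in gene expression between the two measured time points within the group of patients", combined with an FDR below 2%. The wording offers these criteria as examples, and the same section leaves the SAM score threshold adjustable.

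**The concern.** The figure of 2 does two jobs. In 9.3 it is the true change; in 9.4.1.2 it is a bar that the observed change must clear. An estimate centred on the bar clears it about half the time, so a rule that includes the bar cannot select such a gene more often than that. The power calculation includes neither the bar nor the 2% FDR.

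The selected genes feed the clustering, the PAM predictor, the pathway review (9.4.1.2) and the comparison by background regimen (9.4.3.1, item 3). A reader of 9.3 would expect most 2-fold genes to reach those steps. Under the criteria named in 9.4.1.2, at least about half would not.

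**Working it through.** **1. Reproduce the table.** The documents do not give the on-line calculator's formula, so the noise model is an assumption: log-normal expression with SD = √(biological² + technical² + (1/signal-to-noise)²), a true difference of ln 2 = 0.693, and a two-sided rank-sum test at 0.01. There were 6,000 simulations per row (simulation error about √(0.25/6000) = 0.6 points). The first SD is √(0.16 + 0.09 + 0.111) = 0.601. The standard error (SE) of the log fold change is SD × √(2/n).

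| n per time point | Technical SD | Signal-to-noise | SD | SE | Power in 9.3 | Rank test alone | Plus observed change ≥ 2-fold |
|---|---|---|---|---|---|---|---|
| 20 | 0.3 | 3 | 0.601 | 0.190 | 77% | 79% | 50.5% |
| 20 | 0.4 | 3 | 0.657 | 0.208 | 68% | 69% | 49.4% |
| 20 | 0.3 | 2 | 0.707 | 0.224 | 61% | 61% | 47.4% |
| 25 | 0.3 | 3 | 0.601 | 0.170 | 88% | 89% | 50.3% |
| 25 | 0.4 | 3 | 0.657 | 0.186 | 80% | 83% | 49.7% |
| 25 | 0.3 | 2 | 0.707 | 0.200 | 75% | 75% | 49.3% |

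A second model, with additive noise on the raw scale, matched the table within 2 points (77/67/60/88/80/74%) and gave 49/47/46/50/49/49% with the cut. The table is therefore per-gene power at 0.01 with no fold cut and no FDR threshold.

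**2. Why there is a ceiling.** On the log scale, P(observed ≥ 2-fold | true 2-fold) = Φ((ln 2 − ln 2)/SE) = Φ(0) = 0.50. SE cancels, so neither more samples nor pairing moves it. In the additive-noise model at n=100 the test alone has about 100% power, yet the cut keeps 49%.

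**3. Larger true changes.** For a true 3-fold change, (ln 3 − ln 2)/SE = 0.405/0.190 = 2.1 in the first row and 0.405/0.224 = 1.8 in the third, so the cut is passed about 98% and 96% of the time. In the additive-noise model at n=20, p<0.01 plus the cut selects 80-87% at 2.5-fold and 95-98% at 3-fold.

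**4. Add the FDR criterion.** With 500 changed and 37,500 unchanged genes, FDR = 37,500α / (37,500α + 500 × power). At α = 0.01 and 77% power this is 375/(375 + 385) = 49%, far from 2%. Setting FDR to 2% gives α = (0.02/0.98) × (500/37,500) × power = 0.00027 × power. Using t-tests in the log-normal model, all 500 genes truly 2-fold, and the FDR threshold set before the fold cut:

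| Setting (table row order) | FDR <2% alone | FDR <2% plus observed 2-fold |
|---|---|---|
| n=20, unpaired | 24/12/6% | 23/12/6% |
| n=25, unpaired | 47/32/19% | 42/31/19% |
| n=20, paired, assumed correlation 0.5-0.7 | 36-97% | 32-51% |

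Repeat runs differ by about a point, giving unpaired ranges with the cut of roughly 5-24% at n=20 and 18-43% at n=25. The 51% is the 50% ceiling plus simulation error. With the rank-sum test and additive noise the n=25 figures are lower: 28/14/7%.

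**The case against.** The strongest reply is that the fold cut is not what limits power. In the unpaired setting of the 9.3 table at n=20, the FDR criterion does nearly all the work: adding the cut removes at most 0.4 points. Dropping the cut would not restore 60-80% there. This stands, and it is why 50% must be read as a ceiling. The cut binds mainly when pairing raises power. Section 9.3 speaks of within-patient comparisons, but the documents give no within-patient correlation.

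A second reply is that the cut is offered as an example, the SAM threshold is adjustable, and the trial is a pilot claiming only fair power. This also stands in part: if the cut is dropped or set below 2, the ceiling goes. But 2-fold is the only fold criterion named, and the 60-80% remains a claim about the primary endpoint.

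A minimum fold change is also a legitimate relevance screen. Agreed: the point is that power must be computed for the rule used, not that a screen is wrong.

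A reader might infer that real changes below 2-fold are almost always lost because of the cut. In the unpaired log-normal model at n=20, a 1.5-fold gene passes the cut 7-10% of the time, but it meets FDR 2% only 0.4-1.9% of the time without any cut. The loss cannot be put down to the cut alone.

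**Conclusion.** The concern holds as a mismatch between the power statement and the selection rule. The 60-80% is correct for a rank-sum test at 0.01 alone; there is no arithmetic error in the table. It does not describe selection under the criteria named in 9.4.1.2. If the observed 2-fold cut is used, selection of a gene whose true change is exactly 2-fold cannot exceed about 50% at any sample size, paired or not, and the FDR criterion can take it well below that.

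Two stronger readings are not supported. One is that power is about 50% at any n: under the full rule it depends strongly on n, correlation and error rate. The other is that 80% power is reached near a true 2.4-fold change: at n=20 a true change of 2.35-2.41-fold gives 80% passage of the fold cut only. With FDR below 2% as well, a 2.4-fold gene is selected about 55/34/20% of the time in the unpaired log-normal model. Neither figure belongs in 9.3 as power.

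The ceiling assumes an observed fold change that is about median-unbiased, such as a difference in log means or a ratio of means. With a ratio of medians under additive noise it was about 44-45% at n=20-25. The figures below the ceiling rest on the assumed noise models, 500 changed genes all at 2-fold, and the assumed correlations.

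**What to change.** Before any expression data are seen:

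1. In 9.4.1.2, state the selection rule as fixed. Either (a) select on the SAM FDR alone and report fold change with a confidence interval as description, or (b) keep the observed 2-fold cut alongside FDR below 2%.
2. In either case, replace the 60-80% statement in 9.3 with power under that full rule: FDR below 2%, the fold cut if kept, 20 training pairs, and the within-patient correlation stated as an assumption and shown over a range.
3. If the cut is kept, state that the chance of selecting a truly 2-fold gene is capped at about 50%, and show power for larger true changes as well.

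The cost is wording and a recalculation; no patients, samples or procedures are added. Under (a) the gene list may be longer, though hardly so if power is as low as in the unpaired model at n=20. Under either option the stated power may be less favourable.
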